## NOTES:

- Treatment emergent SAEs/AESIs, as per this definition, are included in the summary tables of TEAEs.
- See Section [12.6.2](#) for definition of start of subsequent anti-cancer therapy.

- Note, if a participant crosses over to combination therapy before an AE is resolved, the actual AE end date should still be populated in the AE listings for the monotherapy cohort (regardless of whether the AE worsened on crossover combination therapy).
- As per the protocol, SAEs that are related to study participation will be collected from the time of consent. Note that these will be included in listings (as listings include all AEs), however, will not be included in the tables (as tables only include treatment related AEs).

## 12.5. Appendix 5: Data Display Standards & Handling Conventions

### 12.5.1. Reporting Process

Software	

 
• Prior to October 2023: The latest supported versions of SAS and R software were used.
 
• October 2023 onwards: Latest versions of METEOR and Domino with in-built containers for SAS and R environments will be used. 
 
• As of the 22-Mar-2024, the current versions are METEOR v4.0 and Domino v5.7.1.
 
 
 
	
Reporting Area (prior to October 2023)	
HARP Server	: US1SALX00259
HARP Compound	: Compound: GSK3745417, Study: mid208850
Reporting Area (October 2023 onwards)	
GitHub Repository	gsk_tech/52018_208850 (github.com)
METEOR	IB: 52018_208850_ISRC_<<X>> CSR: 52018_208850_EOS
Analysis Datasets	

 
• Analysis datasets will be created according to CDISC standards (ADaM Version 2.1 and ADaM IG Version 1.1).
 
	
Generation of RTF Files	

 
• RTF files will be generated for all summary tables
 
	

### 12.5.2. Reporting Standards

General	

 
• The current GSK Statistical Display Standards will be applied for reporting, unless otherwise stated (Library Location: https://myteams.gsk.com/:w:/r/sites/IDSLLibrary): 
 
• Section 4: Principles for All Displays
 
• Section 5: Principles for Data Listings
 
• Section 6: Principles for Summary Table
 
• Section 7: Principles for Graphics
 
 
 
	
GSK Statistical Display Principles will be followed in the creation of GSK standard and non-standard outputs	
Formats	

 
• GSK IDSL Statistical Principles for decimal places (DP's) will be adopted for reporting of data based on the raw data collected, unless otherwise stated.
 
• Numeric data will be reported at the precision collected on the eCRF.
 
• The reported precision from non eCRF sources will follow the IDSL statistical principles but may be adjusted to a clinically interpretable number of DP's.
 
• Summary Statistics: values will be reported relative to the precision on the eCRF. Min and max will be to the same as the raw data, mean and median to 1 extra decimal place, standard deviation to 2 extra decimal places.
 
• Listings: values will be displayed to the same precision on the eCRF
 
	

Planned and Actual Time	

 
• Reporting for tables, figures and formal statistical analyses: 
 
○ Planned time relative to dosing will be used in figures, summaries, statistical analyses and calculation of any derived parameters, unless otherwise stated.
 
○ The impact of any major deviation from the planned assessment times and/or scheduled visit days on the analyses and interpretation of the results will be assessed as appropriate.
 
 
 
• Reporting for listings: 
 
○ Planned and actual time relative to study drug dosing will be shown in listings.
 
○ Unscheduled or unplanned readings will be presented within the participant listings.
 
 
 
	
Unscheduled Visits	

 
• Unscheduled visits will not be included in summary tables and/or figures except for worst-case post – baseline analysis and PK data. For PK Unscheduled visits, compare the PK collection time with the corresponding treatment prior to collection of PK. If the PK start date is greater than the latest previous exposure date and less than the immediate next exposure date, then unscheduled PK record will be slotted into the week of previous exposure date. For e.g. if there is an unscheduled PK collection after WEEK 2 treatment exposure and before WEEK 3 treatment exposure, then the unscheduled PK record will be slotted into WEEK 2.
 
• Unscheduled timepoints that fall outside of the protocol defined timepoints after slotting will not be included in the reporting of summary tables for PK.
 
• All unscheduled visits will be included in listings.
 
	
Descriptive Summary Statistics	
Continuous Data	Refer to GSK Statistical Display Standards Section 6.6
Categorical Data	N, n, frequency, %
Graphical Displays	

 
• Refer to GSK Statistical Display Standards Section 7
 
	

### 12.5.3. Reporting Standards for Pharmacokinetic

Pharmacokinetic Concentration Data	
PC Windows Non-Linear (WNL) File	
PC WNL file (CSV format) for the non-compartmental analysis by Clinical Pharmacology Modelling and Simulation (CPMS) function will be created according to the “Standards for the Reporting of PK data using HARP” and “Extraction and Analysis of Pharmacokinetics Data” documents.
 
Note: Concentration values will be imputed as per Non-Compartmental Analysis of Clinical Pharmacokinetic Data (VQD-REF-015788 [1.0]), Section 2.2.3.

Descriptive Summary Statistics, Graphical Displays and Listings	
Refer to IDSL PK Display Standards.
 
Note: Concentration values will be imputed as per Non-Compartmental Analysis of Clinical Pharmacokinetic Data (VQD-REF-015788 [1.0]), Section 2.2.3 for descriptive summary statistics/analysis and summarized graphical displays only. In the

	listing, NQ values will be reported as NQ and the LLQ for the assay will be given (no imputation will be performed).
Pharmacokinetic Parameter Data	
Is NQ impacted PK Parameters Rule Being Followed	Yes, refer to Non-Compartmental Analysis of Clinical Pharmacokinetic Data (VQD-REF-015788 [1.0]), Section 2.3.6.
Descriptive Summary Statistics, Graphical Displays and Listings	Refer to IDSL PK Display Standards. Refer to Non-Compartmental Analysis of Clinical Pharmacokinetic Data (VQD-REF-015788 [1.0]), Section 2.3.6.

## 12.6. Appendix 6: Derived and Transformed Data

### 12.6.1. General

Multiple Measurements at One Analysis Time Point

 
Mean of the measurements will be calculated and used in any derivation of summary statistics but if listed, all data will be presented except for PK. For PK data, if there are multiple records observed at the same date and time for a participant, those data will be excluded from the WNL file and will not be used for the derivation of PK parameters.
 
If there are two values within a time window (as per Section 12.3.1) the value closest to the target day for that window will be used. If values are the same distance from the target, then the mean will be taken. Participants having both High and Low values for Normal Ranges at any post-baseline visit for safety parameters will be counted in both the High and Low categories of “Any visit post-baseline” row of related summary tables. This will also be applicable to relevant Potential Clinical Importance summary tables.
 
PK concentration samples that are duplicated based on the same USUBJID, VISIT, PCTPT and PCDTC variables, are excluded from all PK analyses and displays, including the PK concentration listing, as the duplication is an error. That is, only one unique record according to USUBJID, VISIT, PCTPT, PCDTC and PCORRES is included.
 

Study Day and Period Day

Study Day:
 
 
Study Day is calculated as the number of days from First Dose Date: 
 
Ref Date = Missing → Study Day = Missing
 
Ref Date < First Dose Date → Study Day = Ref Date – First Dose Date
 
Ref Date ≥ First Dose Date → Study Day = Ref Date – (First Dose Date) + 1
 
 
 

Period Day:
 
 
For monotherapy participants who do not crossover, or for participants who join the study in Part 2A/the Imaging Sub-study: the Period Day is the same as the Study Day.
 
For participants who cross over from monotherapy to combination therapy: 
 
Monotherapy period: Period Day is the same as the Study Day.
 
Combination (crossover) period: Period Day is calculated as the number of days from First Combination Dose Date, using the same logic as above.
 
 
 

Change from Baseline

 
Change from Baseline = Post-Baseline Visit Value – Baseline
 
% Change from Baseline = <math>100 \times (\text{Post-Baseline Visit Value} - \text{Baseline}) / \text{Baseline}</math>
 
Maximum Increase/Decrease from Baseline = maximum (Increase/Decrease from Baseline)
 
If either the Baseline or Post-Baseline Visit Value is missing, Change from Baseline and % Change from Baseline is set to missing
 

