### 9.1. Drug Concentration Measures

Blood sampling time will be related to the start of dosing.

GSK3745417 plasma serum concentration-time data will be listed by treatment group. The listing will include treatment group, site ID, unique subject ID, subject ID, age, sex, race detail, visit, date, study day, period day, actual dose (mg), planned relative time, actual time, time deviation, actual relative time, lower limit of quantification (LLQ) value for the assay, concentration results and PK analysis exclusion flag. Values below the LLQ are recorded as Not Quantifiable (NQ), see Section 12.5.3.

The PK analysis exclusion flag indicates which samples are excluded from the PK concentration tables and figures and the PK parameter analysis. In general, the following samples will be excluded:

- Where VISITNUM is missing.
- When PCDTC is missing.
- Pre-treatment pre-dose records (e.g. Week 1) with quantifiable results: pre-treatment pre-dose records should have NQ and those records are included in the PK concentration tables and figures.
- Post-treatment pre-dose records (e.g. Week 2+) with higher PK concentration than final record from previous treatment cycle (e.g. Week 1 EOI+24 HR)

The final list of exclusions (that is, samples that will have the PK analysis exclusion flag as “Yes”) will be provided by CPMS.

GSK3745417 plasma concentration-time data will be summarized by treatment and nominal time using descriptive statistics (n, number imputed, mean, 95% confidence interval [CI], standard deviation [StD], median, minimum, and maximum). If more than 30% of values at a time-point are imputed, then standard deviation will not be reported.

Linear and semi-logarithmic individual concentration-time profiles (by treatment and participant) and mean (+StD) and median profiles by GSK3745417 dose will be plotted.

For the table and figures, NQ values will be imputed as per Section 12.5.3.

Urine concentration data will be made available in RAPIDO DV, see Section 1, when available for participants.

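### SAP Section 12.6.1 gives conflicting rules for duplicate PK records and no order between them, so a valid sample could be lost and displays and PK parameters can rest on different records

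*SAP*

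**What the plan says.** Both rules stand in SAP Section 12.6.1, under the entry "Multiple Measurements at One Analysis Time Point".

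- **First bullet.** When several PK records of one participant carry an identical collection time, "those data will be excluded from the WNL file and will not be used for the derivation of PK parameters". The trigger is participant plus date and time. No record is kept, and identical copies are not exempted. The bullet does not say what happens to these records in the concentration table or figures.
- **Third bullet, first sentence.** The trigger is "PK concentration samples that are duplicated based on the same USUBJID, VISIT, PCTPT and PCDTC variables", a key of four variables. Such samples "are excluded from all PK analyses and displays, including the PK concentration listing, as the duplication is an error".
- **Third bullet, second sentence.** Offered as an explanation of the first, it says that "only one unique record according to USUBJID, VISIT, PCTPT, PCDTC and PCORRES is included". The key now has five variables, with PCORRES added, and one record survives.

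Section 9.1 describes one flag for all uses: "The PK analysis exclusion flag indicates which samples are excluded from the PK concentration tables and figures and the PK parameter analysis". Its four general criteria do not mention same-time or duplicated records, although the final exclusion list comes from the clinical pharmacology group.

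**The concern.** An exact copy of a PK record meets both triggers. For the non-compartmental analysis (NCA) input, the first bullet leaves no record and the third leaves one. The SAP gives neither precedence nor processing order, so two programmers could follow the text and build different input files.

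The third bullet has a second problem. Its two sentences use different keys, and for two records at the same time and time point with different results they lead to opposite outcomes: both removed everywhere, or both kept.

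Cmax and AUC(0-tau) are named in the secondary endpoint (Section 2.2). Table 3 takes Cmax directly from the observed concentrations, so a lost peak is not recovered. Dose-normalized Cmax and AUC also feed the dose-proportionality plots (Section 9.2.2). Apart from any loss, a concentration table and a parameter table that rest on different records cannot be reconciled by a reader of the report.

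**Working it through.** The SAP states no figure to reproduce. The check applies the rules literally to a small assumed profile and counts what survives.

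**Inputs (all concentrations are assumptions).** One participant, one visit, four valid samples: pre-dose 0, end of infusion 10, 1 h 5, 4 h 1. The true Cmax is 10. A fifth record is added at the end-of-infusion date and time.

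**Rules.**
- R1 (first bullet): drop every record that shares participant and date/time with another.
- R3a (third bullet, first sentence, read literally): drop every record that shares the four-variable key with another.
- R3b (third bullet, second sentence): keep one record per five-variable key.

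**Results.**

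| Fifth record | NCA: R1 on raw data | NCA: R3b, then R1 | Displays under R3b | Displays under R3a |
|---|---|---|---|---|
| Exact copy (10) | 3 records, Cmax 5 | 4 records, Cmax 10 | 4 records | 3 records |
| Same time point, different result (12) | 3 records, Cmax 5 | 3 records, Cmax 5 | 5 records | 3 records |
| Same date/time, different PCTPT (10) | 3 records, Cmax 5 | 3 records, Cmax 5 | 5 records | 5 records |

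**Reading the rows.**
1. *Exact copy.* The outcome depends on order. R1 on raw data removes both copies and the peak with them, while the displays keep it under R3b. With R3b first, no same-time records remain, R1 is not triggered, and NCA and displays agree.
2. *Same time point, different result.* R1 removes the pair from the NCA in either order. The displays hold both values under R3b and neither under R3a, which extends to the listing and would leave no trace of the samples.
3. *Same date/time, different time-point label.* The third bullet is not triggered under either key. The NCA loses both records and the displays keep both.

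In rows 2 and 3 the mismatch between R3b displays and NCA does not depend on order.

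**Illustration of size.** If the lost record is the end-of-infusion peak and the next sample comes Δt later, the shortfall in Cmax is 1 − 2^(−Δt/t½):
- Δt 0.25 h, t½ 2 h: 1 − 2^(−0.125) = 8.3%
- Δt 0.25 h, t½ 1 h: 1 − 2^(−0.25) = 15.9%
- Δt 0.5 h, t½ 2 h: 1 − 2^(−0.25) = 15.9%
- Δt 0.5 h, t½ 1 h: 1 − 2^(−0.5) = 29.3%

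The half-lives and gaps are assumed. The SAP says only that the half-life is short (Section 12.6.2).

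**The case against.** The strongest reply is that the third bullet is the specific rule for erroneous copies and the first is the general rule for several records at one time. The third bullet is not limited to tables: it names all PK analyses, so it reaches the NCA. On that reading copies are cleared first, the first bullet then finds nothing to act on, and the valid sample stays in both places. A reader might infer from the first bullet alone that any double entry will delete a valid sample from Cmax and AUC while it still shows in the concentration table. The SAP does not support that as a certainty. It requires the keep-one rule to be applied to the table but not to the NCA, although the bullet covers both. What stands is that the order is not written down and the first bullet contains no exemption.

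Second, for pairs with different results the key makes no difference to Cmax or AUC, because the first bullet removes both records either way. This is correct, and it confines that part of the point to the displays and to their agreement with the parameters. The second bullet also provides for choosing or averaging values within a slotting window, so keeping both is not assured for slotted samples.

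Third, internal standards for the input file (Section 12.5.3), the final exclusion list (Section 9.1) and database cleaning (Section 3.3) might catch such records. They might, but the first are not shown, and none of them changes what Section 12.6.1 instructs.

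Finally, the percentages hold only when the lost sample is the peak. Losing another sample leaves Cmax unchanged and can move AUC in either direction. This stands in full.

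**Conclusion.** The rules conflict as written, and the point is minor. For an exact copy, loss of a valid sample from Cmax and AUC is possible, not certain: it happens if the first bullet is run before de-duplication and does not if copies are removed first. For same-time records that differ, the first bullet always takes them out of the NCA, while the third bullet's second sentence leaves them in the concentration displays; its first sentence could instead remove a same-time-point pair even from the listing.

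The SAP does not say how many such records exist. The number is probably small, but that is a judgement. The range of 8.3% to 29.3% illustrates one lost peak under assumed half-lives and sampling gaps; it does not estimate bias in the secondary endpoint, and no effect on AUC was computed.

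**What to change.** Replace the two PK rules in Section 12.6.1 with one ordered rule:

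1. De-duplicate first on USUBJID, VISIT, PCTPT, PCDTC and PCORRES. Keep one record everywhere, including the WNL file. Delete the four-variable version of the key.
2. Limit the first bullet to records that still share a participant's date and time after step 1 and differ in result or time-point label.
3. Exclude those records from parameter derivation, concentration tables and figures alike, through the PK analysis exclusion flag, and add this criterion to the list in Section 9.1.
4. Show them, flagged, in the concentration listing (Listing 24).

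The cost is a few sentences in the SAP and a de-duplication step before the WNL file is written. No new data are needed.

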## 12.6.2. Study Population

Treatment Assignment	

 
As defined in Section 0, in the All Treated analysis set participants will be assigned to the cohort of the first dose they received, regardless of any permanent dose reductions or regimen changes. This will be derived from exposure data.
 
If the dose level is reduced or the dose regimen changes during the treatment period from what the participant initially received, study population and safety data will be summarized by the dose level the participant initially received. However, PK data will be summarized by the actual dose received for each visit, see below.
 
The most common dose regimen change (within either Part 1A or Part 2A) is expected to be a reduction in frequency, that is, reduction from Q1W dosing to Q3W dosing.
 
Data on participants who have crossed over from Part 1A to Part 2A will generally be presented separately in crossover cohorts, see Section 6.1.3 for details.
 
	
Treatment Assignment: PK	

 
For PK summaries and analyses, participants are assigned to the cohort of the actual dose received at that visit.
 
CCI
 
	

 
Participants who receive <90% of the planned dose level for a specified visit will have their data excluded from the relevant tables and figures for that visit (as it cannot be assigned to an existing cohort).
 
CCI
 
	

schedule while they are on monotherapy. This is due to a limitation in data collection, as regimen change during the study was not collected on the eCRFs. Due to the short half-life of GSK3745417, this treatment assignment approach should have a negligible impact on the PK analyses.
	
Time since Initial Diagnosis	

 
Calculated as the number of [Days] from the Date of Initial Diagnosis: 
 
First Dose Date = Missing → Elapse Time = Missing
 
Date of Initial Diagnosis = Completely/partially Missing → Elapse Time = Missing
 
Otherwise → Elapse Time = First Dose Date – Date of Initial Diagnosis + 1
 
 
 
	
Start of Subsequent Anti-Cancer Therapy	

 
The start of subsequent anti-cancer therapy is defined as the first anti-cancer therapy taken on the same day as or after the last dose of treatment.
 
The following records are included for consideration of anti-cancer therapy: 
 
Systemic therapy: Any systemic therapy, as adjudicated by the clinical team.
 
 
 
	

- **Medical/surgical procedures:** Any medical/surgical procedure, which is classified as “Cancer related” on the eCRF.

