## **7.8. Follow-Up Anti-Cancer Therapies**

Follow-up anti-cancer systemic therapies will be coded using the GSK Drug coding dictionary. The clinical development team will adjudicate whether the systemic therapies are anti-cancer related and will classify the type of anti-cancer systemic therapy. Only surgery/medical procedures that are classified as cancer related on the eCRF will count as anti-cancer surgical/medical procedures.

Follow-up anti-cancer therapy and follow-up radiotherapy data can be viewed using RAPIDO DV - no static displays will be produced.

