#### 12.4.1.1. Study Phases for Anti-Cancer Therapy

This table should be used for anti-cancer systemic therapy, anti-cancer surgical/medical procedures and radiotherapy.

Study Phase	Definition
Prior	If anti-cancer therapy start date is not missing and is before the first dose of study intervention OR If anti-cancer therapy start date is missing and: 
 
• The anti-cancer systemic therapy comes from the Prior Anti-Cancer Therapy eCRF page.
 
• The anti-cancer surgical/medical procedure comes from the Prior Medical/Surgical procedures eCRF page.
 
• The radiotherapy comes from the Anti-Cancer Radiotherapy eCRF page.
 

On Treatment	If anti-cancer therapy start date is not missing and is on or after the first dose and before the last dose of study intervention (if anti-cancer therapy start day is on the same day as first dose then anti-cancer therapy is assumed to have been taken/Performed after first dose) OR If anti-cancer therapy start date is missing and: 
 
• The radiotherapy comes from the Anti-Cancer Radiotherapy On Treatment eCRF page.
 

Follow-up	If anti-cancer therapy start date is not missing and is on or after the last dose of study intervention (if anti-cancer therapy start day is on the same day as last dose then anti-cancer therapy is assumed to have been taken/Performed after last dose) OR If anti-cancer therapy start date is missing and:

Study Phase	Definition
	
 
• The anti-cancer systemic therapy comes from the Follow Up - Anti-Cancer Therapy eCRF page.
 
• The radiotherapy comes from the Follow Up – Radiotherapy eCRF page.
 

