	
 
• If the AE does not worsen, the AE will only be counted in the monotherapy cohort.
 
• If the AE does worsen, then the AE will be counted in both the monotherapy cohort and the crossover combination cohort.
 
 
Note that TDV date is taken as the latest TDV assessment date.
 
For SAEs/AESIs in GSK3745417 monotherapy cohorts:
 
 
• Monotherapy participants who do not crossover: Study Treatment Start Date <math>\leq</math> SAE/AESI Start Date or pre-existing (prior to exposure) SAE/AESI Worsening Date <math>\leq</math> Study Treatment Stop Date + 90 days or Start of Subsequent Anti-Cancer Therapy, whichever occurs first
 
• Monotherapy participants who crossover: Study Treatment Start Date <math>\leq</math> SAE/AESI Start Date or pre-existing (prior to exposure) SAE/AESI Worsening Date <math>\leq</math> the earliest of (Study Treatment Stop Date + 90 days, Start of Subsequent Anti-Cancer Therapy, Crossover Date)
 
• SAE/AESI Start Date is missing
 
 
For SAEs/AESIs in GSK3745417 + dostarlimab combination cohorts:
 
 
• Study Treatment Start Date <math>\leq</math> SAE/AESI Start Date or pre-existing (prior to exposure) SAE/AESI Worsening Date <math>\leq</math> Study Treatment Stop Date + 90 days or Start of Subsequent Anti-Cancer Therapy, whichever occurs first
 
• SAE/AESI Start Date is missing
 
 
For SAEs/AESIs in GSK3745417 + dostarlimab crossover cohorts:
 
 
• (Crossover) Combination Study Treatment Start Date <math>\leq</math> SAE/AESI Start Date or SAE/AESI Worsening Date for SAE/AESI that started during the GSK3745417 monotherapy cohort <math>\leq</math> (Crossover) Combination Study Treatment Stop Date + 90 days or Start of Subsequent Anti-Cancer Therapy, whichever occurs first.
 
• SAE/AESI Start Date is missing
 
 
CCI

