**CONFIDENTIAL**

Element	Reporting Detail
	CCI
Concomitant Medications/ Medical History	
Prior Anti-cancer Systemic	

Element	Reporting Detail
Therapy/ Radiotherapy/ Surgical Procedures	CCI
Follow-up Anti-cancer Systemic Therapy (as adjudicated by the clinical team)/Cancer related Surgical Procedures for Efficacy Evaluation (BOR) and TEAE definition	
Other Follow- up Anti-cancer Systemic Therapy/ Radiotherapy/ Non-cancer related Surgical Procedures	
On-treatment Radiotherapy	CCI

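### Any procedure marked cancer related can close the 90-day SAE/AESI window, because SAP Section 12.6.2 does not check it for anti-tumour intent

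*SAP*

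**What the plan says.** SAP Section 12.6.2 takes the date of the first qualifying record on or after the day of the last dose. Two record types qualify. The first is "Any systemic therapy, as adjudicated by the clinical team". The second is introduced by "Any medical/surgical procedure, which is classified as", and the class named is the eCRF's cancer-related category.

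Section 7.8 applies the same test to follow-up procedures: "Only surgery/medical procedures that are classified as cancer related on the eCRF will count as anti-cancer surgical/medical procedures". The adjudication in Sections 7.6 and 7.8 is described for systemic therapies only.

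Section 12.4.2 uses the date for SAEs and AESIs. Their treatment-emergent window runs to 90 days after treatment stop or "Start of Subsequent Anti-Cancer Therapy, whichever occurs first". For monotherapy participants who cross over, the crossover date is a further limit. Events that are neither SAEs nor AESIs follow another rule: the window runs to the treatment discontinuation visit (TDV), or to 30 days after treatment stop if the TDV is missing, and subsequent therapy does not shorten it.

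In Section 12.7.2.1 the label of one missing-date row pairs adjudicated systemic therapy with "Cancer related Surgical Procedures for Efficacy Evaluation (BOR) and TEAE definition". Under Section 8.2, summary tables show treatment-emergent events only, while listings show all adverse events.

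**The concern.** A procedure can relate to a cancer without treating it. Diagnostic, access and drainage procedures are examples. These are illustrations supplied here; the SAP names none of them. Nothing visible in Section 12.6.2 or 7.8 stops such a record from counting as new anti-cancer therapy if the site classifies it as cancer related. Systemic therapy passes through a filter that procedures do not.

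Closing the window early makes sense when a new treatment could explain later events. That reason is absent when the procedure was not a treatment. The SAE or AESI would still be left out of the treatment-emergent counts. Incidence and severity of adverse events is a primary endpoint (Section 2.2), and late immune-related events are among those the 90-day window exists to capture. The flag feeds the AESI and CRS/infusion-reaction tables (3.8 and 3.9), the serious-event tables (3.10 to 3.13) and the overall treatment-emergent tables. Several of these also go into the Investigator Brochure.

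**Working it through.** The SAP states no figure to reproduce. The check traces the definition to its use and then works out what the rule does.

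**Inputs**
- Records that count: Section 12.6.2 (adjudicated systemic therapy; any procedure marked cancer related).
- SAE/AESI window: 90 days after treatment stop, or the start of subsequent therapy if earlier (Section 12.4.2).
- Window for other adverse events: to the TDV, or 30 days after treatment stop if the TDV is missing (Section 12.4.2).
- Procedure day d, counted from the last dose: assumed, because the documents give no distribution.

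**Step 1: is there a test of intent?** Section 7.8 makes the eCRF classification a condition for counting a procedure and adds no other. Section 12.6.2 admits any procedure so classified. The footnote to Table 1.14, which covers prior therapy, says that the investigator makes this classification. None of these places requires anti-tumour intent.

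**Step 2: how much of the window is lost?** Post-dose days remaining = min(90, d). For d up to 90, days lost = 90 − d and share lost = (90 − d)/90.
- d = 0: 90 days lost (100%). Same-day records count, so only events on the last-dose day itself remain.
- d = 10: 90 − 10 = 80 days lost, 80/90 = 89%.
- d = 14: 90 − 14 = 76 days lost, 76/90 = 84%.
- d = 30: 90 − 30 = 60 days lost, 60/90 = 67%.

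**Step 3: comparison with ordinary adverse events.** With the TDV missing, ordinary events count to day 30. The SAE/AESI window is the shorter of the two whenever d < 30, by 30 − d days. With d = 2 the difference is 30 − 2 = 28 days. An ordinary event on day 10 is then treatment-emergent, while an immune-related SAE on day 10 is not. If a TDV is recorded, the same reversal occurs whenever the procedure precedes it. The events given the longer window can end up with the shorter one.

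**Step 4: what is untouched?**
- Events before the last dose: only procedures on or after that day count.
- Events with a missing start date: always treatment-emergent (Section 12.4.2).
- The DLT summary: it uses the determinative period (Section 8.2.4).
- The death summary: it covers all deaths (Section 8.2.2).
- Listings: they keep every adverse event, and the listing of all adverse events carries the treatment-emergent flag.

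**The case against.** The strongest reply is that the eCRF classification is itself an investigator's judgement, and that Sections 7.6 and 7.8 deliberately use it as the test for an anti-cancer procedure. The completion guidance is not shown and may tell sites to reserve the category for treatment of the tumour. Section 12.6.2 also introduces its two record types as records for consideration, which might imply some later screening. These points stand as limits: the loss is possible under the wording, not shown to occur. They do not close the gap, because no later screening of procedures is described anywhere visible, while screening of systemic therapy is.

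A second reply is that follow-up under Protocol Amendment 7 also ends at subsequent anti-cancer therapy (Sections 7.2 and 12.7.1), and that the protocol's definition of that term is not at hand. This also stands, and bears on how the fix is worded.

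A reader might go further and treat the absence of radiotherapy from Section 12.6.2 as an error. The documents do not support that. The row labels in Section 12.7.2.1 leave it out in the same way, placing follow-up radiotherapy in a separate row. Section 12.4.1.1 covers radiotherapy ("This table should be used for anti-cancer systemic therapy, anti-cancer surgical/medical procedures and radiotherapy"), but that table only assigns records to study phases and does not define when subsequent therapy starts. Leaving radiotherapy out keeps the SAE/AESI window open, which is the conservative direction for safety counts.

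A reader might also infer that radiation-induced shrinkage could be credited as response. The efficacy section and the relevant cells of Section 12.7.2.1 are redacted, so the rule for best overall response cannot be judged.

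**Conclusion.** The point holds for procedures and for the SAE/AESI flag. As written, a procedure with no anti-tumour purpose can end the window on the day it takes place if the site marks it cancer related, and later SAEs and AESIs then leave the summary tables. For an affected participant the loss is 90 − d days, up to the whole post-dose window. At trial level its size is unknown: the documents do not give the number of such procedures or say how sites use the category.

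It should not be read as a loss of safety data, since the events stay in the listings, or as a threat to the DLT results. It is a bounded weakness in the counting of SAEs and AESIs after the last dose. It merits correction because the remedy is specific and cheap. The conclusion rests on the visible text of Sections 7.8, 12.4.2 and 12.6.2, and on the assumption that eCRF guidance does not already restrict the category to tumour-directed procedures.

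**What to change.** In Section 12.6.2, count a procedure marked cancer related and dated on or after the last dose only if the clinical team adjudicates it as treatment with anti-tumour intent. This extends the review already done for systemic therapy. State that diagnostic, access and drainage procedures do not count. Bring Section 7.8 and the row label in Section 12.7.2.1 into line. That label also names best overall response, so check the new wording against Section 10. Check it too against the protocol's definition of subsequent anti-cancer therapy, so that the analysis window matches the period in which SAEs and AESIs were collected.

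The cost is SAP wording plus review of a limited number of procedure records before database freeze. Some SAEs and AESIs that follow supportive procedures will re-enter the treatment-emergent tables.
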